3.1 POTENTIAL RISKS

The potential risks of use of the FORMA System are similar to those encountered with standard cardiac catheterization and use of anesthesia and have been listed in two categories below. First, there are the potential complications associated with the overall procedure including standard cardiac catheterization and the use of anesthesia. Second, there are the additional potential risks associated with the use of the FORMA System. Estimated occurrence rankings of the potential risks are provided in the Sample Informed Consent Form in Appendix A.

[REDACTED]

Risks related to the overall procedure including standard cardiac catheterization and the use of anesthesia may include, but may not be limited to, the following:

- abnormal lab values;
- access site AV fistula or pseudoaneurysm;
- allergic reaction to anesthesia or to contrast media;
- anemia;
- angina;
- arrhythmia;
- bleeding;
- cardiovascular or vascular injury including perforation, obstruction, or dissection of valvular structures that may require intervention, including access sites;
- conduction system injury (defect) which may require replacement or implantation of a pacemaker (permanent or temporary);
- death;
- dyspnea (e.g., orthopnea);
- electrolyte imbalance;
- embolization including air, particulate, calcific material, or thrombus;
- exercise intolerance or weakness;
- fever;
- heart failure;
- heart murmur;
- hematoma;
- hemorrhage requiring transfusion or intervention;
- hypertension/hypotension;
- infection, including septicemia and endocarditis;
- inflammation;
- leaflet damage;
- myocardial infarction;
- pain or changes at the access site;
- paralysis;
- pericardial effusion/cardiac tamponade;
- permanent disability;
- pleural effusion;
- pulmonary edema;
- renal failure;
- renal insufficiency;
- reoperation;
- restenosis;
- retroperitoneal bleed;

- skin burn;
- syncope;
- systemic peripheral ischemia/nerve injury;
- thromboembolic events, stroke, transient ischemic attack, clusters, or neurological changes;
- wound dehiscence, delayed or incomplete healing.

In addition to the risks listed above, additional potential risks associated with the use of the FORMA System may include, but may not be limited to, the following:

- cardiac arrest;
- cardiac dysrhythmias requiring replacement or implantation of a pacemaker (temporary or permanent);
- cardiac failure/low cardiac output;
- cardiogenic shock;
- chordal damage, rupture;

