5 STUDY ENDPOINTS

5.1 FEASIBILITY ENDPOINTS

5.1.1 SAFETY ENDPOINT

Composite of major adverse events (MAE) defined as cardiovascular mortality, myocardial infarction, new need for renal replacement therapy, severe bleeding, re-intervention and major access site and vascular complications at 30 days.

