12.4 DEATHS AND EXPLANTS

12.4.1 PATIENT DEATHS

Patient death occurring during the study should be reported to the Sponsor or designee within one (1) business day of Investigator's knowledge of the death. The Adverse Event that resulted in death should be entered in the database on the Adverse Event form within one (1) business day and include a brief description of the relevant clinical information leading to the death of the patient. In the event of patient death, every effort should be made to obtain a copy of the autopsy report and/or death summary. Information on the cause of death and its relationship to the investigational device or study procedure will be determined by the Investigator. Copies of an autopsy report, if available, and/or a death summary are to be forwarded to the Study Sponsor.

If a device is explanted during autopsy, the device should be returned to the Study Sponsor for analysis. Return kits for devices will be provided upon request by the clinical monitor. In addition, patient death must be reported to the IRB in accordance with IRB requirements.

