| 
Death (MVARC)
 | 
Cardiovascular (CV) Death
 
The primary cause of CV death will be categorized using the following choices:
 
 ○ Arrhythmia and/or conduction system disturbance ○ Cardiovascular infection and sepsis (e.g. Endocarditis) ○ Device failure ○ Heart failure ○ Major bleeding ○ Myocardial Infarction ○ Stroke ○ Sudden, unexpected death / unknown ○ Tamponade ○ Thromboembolism ○ Other CV cause 
If death was due to a heart failure, it will be sub classified into:
 
 ○ LV dysfunction ○ RV dysfunction ○ Biventricular dysfunction 
Non-Cardiovascular (CV) Death
 
A diagnosis of non-CV death requires the primary cause to be clearly related to another condition due primarily to an identifiable non-CV cause or etiology. Specific diagnoses may include respiratory failure, pneumonia, trauma, suicide, or any other non-cardiovascular defined causes (e.g., liver disease, malignancies etc.) not included in the previous categories.
 
Primary cause of non-CV death
 
The primary cause of non-CV death will be categorized using the following choices:
 
 ○ Adverse drug reaction or overdose ○ Cancer ○ Gastrointestinal |
|-----------------------------|--|

| | |
|--|--|
| | 
 ○ Liver failure ○ Non-cardiovascular infection and sepsis (e.g. pneumonia) ○ Pancreatic ○ Renal failure ○ Respiratory Failure ○ Trauma ○ Other non-CV cause |
| Device Deficiency (ISO 14155:2011) | An inadequacy of a medical device with respects to its identity, quality, durability, reliability, safety or performance. Device deficiencies include malfunctions, use errors and inadequate labeling. |
| Device Fracture | Break or other structural defect in anchor, railing, or spacer with or without embolization |
| Device Malfunction | Device malfunction is defined in as a failure of an investigational medical device to perform in accordance with its intended purpose when used in accordance with the Instructions for Use. See “Device Deficiency” |
| Device Success | Device is deployed as intended and the delivery system is successfully retrieved as intended at the time of the patient’s exit from the cardiac catheterization laboratory. |
| eGFR | Estimated glomerular filtration rate |

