### 3. STUDY ENDPOINTS

#### 3.1 Safety Endpoints

Composite of major adverse events (MAE) defined as cardiovascular mortality, myocardial infarction, new need for renal replacement therapy, severe bleeding, re-intervention and major access site and vascular complications at 30 days.

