**3.3.2 FDA Procedural Success (at 1 month): Safety**

- Device Success, and
- None of the following device or procedure related SAE's:
  - a) Life threatening bleeding
  - b) Major vascular or cardiac structural complications requiring intervention,
  - c) Pericardial effusion requiring drainage or surgery (includes tamponade),
  - d) Stage 2 or 3 AKI (includes new dialysis).
  - e) Severe heart failure or hypotension requiring IV inotrope, ultrafiltration or MCS.
  - f) Prolonged intubation > 48 hours

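### The death definition has no procedure-related category, so a death that the procedure causes through a non-cardiovascular mechanism may be left out of the 30-day MAE composite

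*Protocol*

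**What the plan says.** Protocol 5.1.1 defines the safety endpoint as "Composite of major adverse events (MAE) defined as cardiovascular mortality, myocardial infarction, new need for renal replacement therapy, severe bleeding", then re-intervention and major access site and vascular complications, all at 30 days. SAP 3.1 uses the same definition. In Protocol 18 the entry for cardiovascular mortality simply points to the entry for Death, so that entry alone settles which deaths count.

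The Death entry sorts by primary cause. For a non-cardiovascular code it says: "A diagnosis of non-CV death requires the primary cause to be clearly related to another condition due primarily to an identifiable non-CV cause" (the sentence then adds etiology as an alternative to cause). The cardiovascular list includes "Device failure", tamponade, major bleeding, sudden or unknown death and an open category for other cardiovascular causes. It has no procedure-related entry. The non-cardiovascular list names adverse drug reaction or overdose, renal failure, respiratory failure and non-cardiovascular sepsis, without an exception when the procedure is the origin.

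Protocol 12.4.1 does collect relatedness: "Information on the cause of death and its relationship to the investigational device or study procedure will be determined by the Investigator". The MAE definition makes no use of it. SAP 8.1 analyses the composite and its components in the as-treated cohort, on adjudicated data.

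**The concern.** Evaluating safety is the first objective in Protocol 4, and the results are meant to guide later study designs. A safety composite for an implant procedure should count a death that the procedure caused.

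The hazards at issue are ones the protocol itself foresees. Protocol 3.1 lists "allergic reaction to anesthesia or to contrast media", septicemia and renal failure among the procedural risks, and pneumothorax among the additional risks of the system. Protocol 8.6 requires general anesthesia for the implant procedure.

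If such a death is coded by its terminal mechanism, it can fall outside cardiovascular mortality and so outside the named safety endpoint. Clinical success is procedural success without an MAE at 30 days, so it inherits the same gap.

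**Working it through.** There is no figure in the plan to reproduce. Protocol 13.1 sets n = 60 without statistical justification, and neither document gives an expected MAE rate or a threshold. The check is therefore a reading of the definitions, followed by the size of one misplaced death.

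**Step 1. Each route against the Death entry and the other MAE components**

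| Cause of a procedure-caused death | Code under Protocol 18 | Other MAE component that could catch it | Result |
|---|---|---|---|
| Contrast or anesthetic reaction | Fits the drug-reaction entry: non-cardiovascular | None specific to it | Likely missed when well documented |
| Respiratory failure | Named non-cardiovascular | None specific to it | Likely missed |
| Renal failure | Named non-cardiovascular | New renal replacement therapy is an MAE by itself | Missed only if no new renal replacement therapy |
| Access-site sepsis | Unsettled: there is a cardiovascular and a non-cardiovascular infection entry | Infection is not among the listed major access-site injuries | Ambiguous |

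Two of the four routes are likely missed, one is missed conditionally, and one cannot be decided from the text.

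**Step 2. Clinical success**

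Protocol 5.1.2.2 needs device success, an EROA reduction of at least 30% from baseline to discharge, and no surgical or percutaneous intervention before discharge. Protocol 5.1.2.3 then needs only the absence of an MAE at 30 days. A patient who meets the first set, leaves hospital, and dies within 30 days of a cause coded non-cardiovascular satisfies both definitions as written. This applies only to deaths after discharge.

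**Step 3. Size of one death**

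Inputs: n = 60 (Protocol 13.1); 30 patients in each enrolment subgroup (SAP 4); 95% Clopper-Pearson intervals (SAP 6.1). The event counts are assumptions.

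Shift per death: 1/60 = 1.7 percentage points; 1/30 = 3.3 points. The analysis is as-treated, so 60 is the largest possible denominator. With an assumed 54 implanted, the shift is 1/54 = 1.9 points.

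Interval for x events in n: lower limit = Beta quantile(0.025; x, n − x + 1), or 0 when x = 0; upper limit = Beta quantile(0.975; x + 1, n − x).

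| Assumed MAE count without the death | With one such death added |
|---|---|
| 0/60 = 0.0% (0.0 to 6.0) | 1/60 = 1.7% (0.04 to 8.9) |
| 6/60 = 10.0% (3.8 to 20.5) | 7/60 = 11.7% (4.8 to 22.6) |
| 0/30 = 0.0% (0.0 to 11.6) | 1/30 = 3.3% (0.08 to 17.2) |

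With two such deaths, 6/60 becomes 8/60 = 13.3% (5.9 to 24.6).

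**Step 4. Chance that the question arises at all**

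For an assumed true rate p of such deaths, P(at least one in 60) = 1 − (1 − p)^60. This gives 45% at p = 1%, 70% at 2%, 84% at 3% and 95% at 5%. The documents offer no basis for choosing p.

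**The case against.** The strongest reply is that counting cardiovascular rather than all-cause deaths is a disclosed choice, applied consistently, and that the Death entry is harder to satisfy for a non-cardiovascular code than it first appears. The primary cause must be clearly tied to an identifiable non-cardiovascular cause or etiology, so an adjudicator may look to origin. Unknown deaths default to cardiovascular, and an open cardiovascular category exists. Fatal access-related vascular injury and fatal cardiac perforation are major complications whatever the death code. All of this stands, and it is why the right verb is *may*. It does not close the gap. A well-documented drug reaction or respiratory failure is identifiable and has its own non-cardiovascular entry, and the open category is undefined.

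Three stronger readings are tempting, and the documents do not support them:

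- A reader might infer that every procedure-caused death of these kinds is coded non-cardiovascular and missed. New renal replacement therapy is an MAE in its own right, and access-site sepsis could be coded under "Cardiovascular infection and sepsis (e.g. Endocarditis").
- A reader might infer that a fatal event scores better than its non-fatal form, because FDA Procedural Success (SAP 3.3.2) fails on "Prolonged intubation > 48 hours" or on stage 2 or 3 AKI. That compares two endpoints. Within FDA Procedural Success the fatal case also fails, since Device Success requires survival. Within the MAE composite, neither prolonged intubation nor AKI without renal replacement therapy counts.
- A reader might infer that the death would disappear from the report. SAP 8.3 tabulates each component of FDA Device Success, including being alive, from 1 month. SAP 8.4.3 summarises serious events up to 30 days for ITT and lists them all.

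The committee charters are not among the documents, and Protocol 15 gives the safety committee's charter precedence. Whether a charter already covers procedure-related deaths cannot be checked here.

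**Conclusion.** The concern holds in this limited form. As written, a death clearly caused by the procedure through an adverse drug reaction, respiratory failure, or renal failure without new renal replacement therapy may be coded non-cardiovascular. It is then missing from the 30-day MAE composite unless another component occurs, and after discharge it can be counted as a clinical success. Where the gap operates, it can only lower the MAE rate. That is not a claim that the death definition as a whole favours the device, because its default for unexplained deaths runs the other way.

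The size is 1.7 points per death at n = 60 and 3.3 at n = 30, with zero such deaths possible. No pass mark for the MAE rate is stated, so no formal decision would change. What is affected is the accuracy of the named safety endpoint. The conclusion assumes that no charter already supplies the missing rule.

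**What to change.** Add to the Death entry in Protocol 18, and refer to it in SAP 3.1 and 8.1:

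> Any death within 30 days that the committee adjudicating MAEs judges to have a probable or causal relationship (Protocol 12.2 scale) to the study device or the implant procedure, including its anesthesia, contrast or access, counts as cardiovascular mortality for the MAE endpoint, whatever the terminal mechanism. Deaths judged possibly related are listed separately.

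The threshold and the adjudicator both need stating. Protocol 12.4.1 records only the investigator's view, and Protocol 12.2 makes possible the default level when relatedness cannot be assessed.

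Show all-cause 30-day mortality beside the composite for the as-treated and ITT populations. The ITT row is needed because the as-treated MAE analysis leaves out a patient who dies after skin incision but before implantation, and the coding rule cannot reach that death.

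The cost is one sentence, one table row per population and one extra adjudication item per death. The MAE rate may become slightly less favourable.

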| MAE | Major adverse event defined as cardiovascular mortality, myocardial infarction, new need for renal replacement therapy, severe bleeding, re-intervention and major access site and vascular complications |
| Malfunction | Refer to ISO 14155 definition |
| Mortality | See "Death" |

Final

| | |
|---|---|
| 
Myocardial Infarction (MVARC)
 | 
 ○ Periprocedural MI (≤48 hours after index procedure procedure)*†: 
A. In patients with normal baseline CK-MB (or cTn):
 
 ○ The peak CK-MB measured within 48 h of the procedure rises to ≥10x the local laboratory ULN (Upper Limit of Normal) PLUS new ST-segment elevation or depression of ≥1 mm in ≥2 contiguous leads (measured 80 ms after the J-point) ○ The peak CK-MB measured within 48 h of the procedure rises to ≥5x ULN with new pathological Q waves in ≥2 contiguous leads or new persistent LBBB ○ In the absence of CK-MB measurements and a normal baseline cTn, a cTn (I or T) level measured within 48 h of the PCI rises to ≥70x the local laboratory ULN PLUS new ST-segment elevation or depression of ≥1 mm in ≥2 contiguous leads (measured 80 ms after the J-point) ○ The peak CK-MB measured within 48 h of the procedure rises to ≥35x ULN with new pathological Q waves in ≥2 contiguous leads or new persistent LBBB. 
B. In patients with elevated baseline CK-MB (or cTn): The CK-MB (or cTn) rises by an absolute increment equal to those levels recommended above from the most recent pre-procedure level plus, new ECG changes as described.
 
 ○ Spontaneous MI (>48 hours after index procedure procedure): 
Detection of rise and/or fall of cardiac biomarkers (preferably cTn) with at least 1 value above the 99th percentile URL (or ULN in the absence of URL) together with at least 1 of the following:
 
  Symptoms of ischemia  ECG changes indicative of new ischemia (new ST-segment or T-wave changes or new LBBB) or new pathological Q waves in ≥2 contiguous leads  Imaging evidence of a new loss of viable myocardium or new wall motion abnormality |
|---|---|

| | |
|--|---|
| | 
○ MI associated with sudden, unexpected cardiac death†: Sudden cardiac death or cardiac arrest, often with symptoms suggestive of myocardial ischemia, and accompanied by presumably new ST-segment elevation or new LBBB and/or evidence of fresh thrombus by coronary angiography and/or at autopsy, but death occurs before blood samples could be obtained or at a time before the appearance of cardiac biomarkers in the blood ○ Pathological findings of an acute myocardial infarction† 
Note:
 
The use of high sensitivity (hs)-troponins is recommended for diagnosis of Type II (spontaneous) MI, but has not been studied for assessment of periprocedural MI. Standard troponin assays are therefore recommended for evaluation of Type I MI
 
Situations where MI is suspected must be carefully evaluated by taking into consideration past medical history, procedural specifics, renal function etc. It is known that cardiac procedures are associated with multiple confounding factors that contribute to myocardial damage
 
*Periprocedural biomarker elevation >ULN not meeting the criteria for MI should be categorized as “myonecrosis not meeting MI criteria.”
 
†Adapted from Moussa et al.
 |
|--|---|

| | |
|---|--|
| New York Heart Association Classification (NYHA Class) | 
Class I: Patients with cardiac disease but without resulting limitations of physical activity.
 
Class II: Patients with cardiac disease resulting in slight limitation of physical activity. Patients are comfortable at rest. Ordinary physical activity results in fatigue, palpitation, dyspnea, or anginal pain.
 
Class III: Patients with cardiac disease resulting in marked limitation of physical activity. They are comfortable at rest. Less than ordinary physical activity causes fatigue, palpitation dyspnea, or anginal pain.
 
Class IV: Patients with cardiac disease resulting in inability to carry on any physical activity without discomfort. Symptoms of cardiac insufficiency or of the anginal syndrome may be present even at rest. If any physical activity is undertaken, discomfort is increased.
 |
| Nonstructural Dysfunction | Abnormality extrinsic to the repair device that results in valve dysfunction (stenosis, regurgitation or both) |
| Pacemaker Dependency | Continuous ventricular stimulation without any pacemaker inhibition by spontaneous cardiac activity determined during the last interrogation within 180 days. |
| Patient | A person with the disease (tricuspid regurgitation) being screened to participate or participating in this clinical study. |
| Peripheral Thromboembolic Event | See "Embolism" |
| Pre-Existing Condition | A pre-existing condition is one that was present prior to clinical study screening. |
| Procedural Success | Procedural success: device success with evidence of TR reduction as evidenced by a relative reduction in EROA of $\geq 30\%$ from baseline to discharge and without the need for a surgical or percutaneous intervention prior to hospital discharge. |
| Prosthesis | An artificial substitute |
| QoL | Quality of Life |
| Reintervention | Any intervention (surgical or transcatheter) on the previously implanted study device (repair, alteration or replacement). |
| Renal Failure | See "Acute Kidney Injury (AKI)" |
| Screen Failure | A patient who has signed the consent but, does not fulfill enrollment criteria: does not meet the inclusion criteria or who meets at least one of the exclusion criteria. |
| Serious Adverse Device Effect (SADE) | Refer to ISO 14155 definition |

| | |
|--|--|
| Serious Adverse Event (SAE) (ISO 14155:2011) | Adverse event that: 
 1. led to death 2. led to serious deterioration in the health of the patient that either resulted in : 
 a. a life-threatening illness or injury, or b. a permanent impairment of a body structure or a body function, or c. in-patient or prolonged hospitalization, or medical or surgical intervention to prevent life threatening illness or injury or permanent impairment to a body structure or a body function. 3. led to fetal distress, fetal death or a congenital abnormality or birth defect (not anticipated in this study as pregnant women are excluded from the study) |
| Severe Bleeding (MVARC) | Severe bleeding is a major, extensive, life-threatening or fatal bleeding. |
| SF-12 | A short survey with 12 questions that results in two scales of mental and physical functioning and overall health related quality of life. |
| Six (6) MWT | Six minute walk test |
| Spacer Migration | Anchor has not migrated from original implanted position, Spacer is no longer within the tricuspid valve (non-therapeutic) |

| | |
|-------------------------------|---|
| Stroke/TIA (MVARC) | 
Stroke
 
1. Acute episode of a focal or global neurological deficit with at least one of the following:
• Change in level of consciousness• Hemiplegia• Hemiparesis• Numbness• Sensory loss affecting one side of the body• Dysphasia or aphasia• Hemianopia• Amaurosis fugax• Other neurological signs or symptoms consistent with stroke2. Duration of symptoms:
• A focal or global neurological deficit \geq 24 hours• A focal or global neurological deficit $<$ 24 hours if available neuroimaging indicates a new intracranial or subarachnoid hemorrhage (hemorrhagic stroke) or central nervous system infarction (ischemic stroke)• The neurological deficit results in death3. No other readily identifiable non-stroke cause for the clinical presentation (e.g. brain tumor, trauma, infection, hypoglycemia, peripheral lesion, pharmacological influences) to be determined by or in conjunction with designated neurologist.*4. Confirmation of the diagnosis by at least one of the following:
○ Neurologist or neurosurgical specialist, or○ Neuroimaging procedure (CT scan or brain MRI)○ Non-neurologist physician (if neurologist is not available)○ Clinical presentation alone 
Stroke etiology will be classified as:
 |
|-------------------------------|---|

| | |
|--|--|
| | 
• Ischemic: an acute symptomatic episode of focal cerebral, spinal, or retinal dysfunction caused by an infarction of the central nervous system tissue• Hemorrhagic: an acute episode of focal or global cerebral or spinal dysfunction caused by intraparenchymal, intraventricular, or subarachnoid hemorrhage• Undetermined: if there is insufficient information to allow categorization as ischemic or hemorrhagic 
Stroke severity
 
• Disabling: mRS score of ≥ 2 at 90 days (or the last available clinical visit with evaluable data) AND an increase in ≥ 1 mRS category from an individual's pre-stroke baseline• Non-disabling: mRS score of < 2 at 90 days (or the last available clinical visit with evaluable data) or doesn't result in an increase in ≥ 1 mRS category from pre-stroke baseline 
It is recognized that an assessment of stroke is incomplete without an appropriate measurement of the disability resulting from the stroke, hence, mRS closest to 90 days post event** will be used to assess clinical disability using the following scale:
 
0 - No symptoms at all 1 - No significant disability despite symptoms (able to carry out all usual duties and activities) 2 - Slight disability (unable to carry out all previous activities but able to look after own affairs without assistance) 3 - Moderate disability (requiring some help, but able to walk without assistance) 4 - Moderately severe disability (unable to walk without assistance and unable to attend to own bodily needs without assistance) 5 - Severe disability (bedridden, incontinent, and requiring constant nursing care and attention) 6 - Dead
 |
|--|--|

| | |
|--|---|
| | 
CEC adjudicator will indicate if there was an increase of mRS since pre-stroke baseline, how much the mRS has increased, and the mRS total score closest to 90 days post Stroke.
 
TIA
 
Acute episode of a focal or global neurological deficit fulfilling the following criteria:
 
1. Resulting in at least one of the following
• Change in level of consciousness• Hemiplegia• Hemiparesis• Numbness• Sensory loss affecting one side of the body• Dysphasia or aphasia• Hemianopia• Amaurosis fugax• Other neurological signs or symptoms consistent with stroke2. Duration of deficit could be one of the following:
• A focal or global neurological deficit < 24 hours• Any available neuroimaging does not demonstrate a new hemorrhage or infarct3. No other readily identifiable non-stroke cause for the clinical presentation (e.g. brain tumor, trauma, infection, hypoglycemia, peripheral lesion, pharmacological influences) to be determined by or in conjunction with designated neurologist.* 
Notes:
 
• If neurological event does not meet the definition of Stroke or TIA, the CEC adjudication will indicate that accordingly on the form.• *Patients with non-focal global encephalopathy will not be reported as a stroke without unequivocal evidence based upon neuroimaging studies. |
|--|---|

| | |
|---|--|
| | 
 **Evaluation of stroke between 30 and 90 days is acceptable if 90-day follow-up not available #If a stroke is reported without evidence of confirmation of the diagnosis by one of these methods, the event may still be considered a stroke on the basis of the clinical presentation alone. |
| Patient | Refer to ISO 14155 definition |
| Patient Withdrawal | A patient who decides not to participate in the study after signing an informed consent form and being enrolled. |
| Thromboembolic Event | See “embolism” |
| Thrombus (Device Thrombosis) | 
An aggregation of platelet, fibrin, clotting factors, and other cellular elements exclusive of infection.
 
Device thrombosis is defined as any thrombus in the absence of infection attached to or near the investigational device that interferes with function of the device. An investigational device related thrombus may be confirmed by operation, autopsy, or diagnostically by such methods as echocardiography, angiocardiography, or magnetic resonance imaging.
 |
| Transient Ischemic Attack (TIA) (MVARC) | See “Stroke/TIA” |
| Tricuspid Regurgitation | Tricuspid Regurgitation (TR), tricuspid insufficiency or tricuspid incompetence describes a condition in which blood flow through the tricuspid valve flows in the incorrect direction during part of the cardiac cycle. |
| Unanticipated Adverse Device Effect (UADE) (FDA) | Any serious adverse effect on health or safety or any life-threatening problem or death caused by, or associated with, a device, if that effect, problem, or death was not previously identified in nature, severity, or degree of incidence in the investigational plan or application (including a supplementary plan or application), or any other unanticipated serious problems associated with a device that relates to the rights, safety, or welfare of patients. |
| Valvular Leak (See Also “Nonstructural Dysfunction”) | Any evidence of leakage of blood through the native valve leaflets and around the investigational device. Diagnosis of valvular leak may be obtained from echo; however definitive diagnosis is obtained at reoperation, explant, or autopsy. |

| | |
|-----------------------------------|--|
| Withdrawal by Investigator | A patient who consents to participate in the study and is enrolled but is withdrawn by the Investigator. |
|-----------------------------------|--|

Final

